10.2.2 Adverse Event Overview

An overall of AEs will be presented consisting of the number and percentage of subjects experiencing at least one event for each of the following AE categories:

- Any treatment-emergent AE
- Any treatment-emergent AE related to study drugs (atogepant and ubrogepant) according to the investigator
- Any severe treatment-emergent AE
- Any serious treatment-emergent AE
- Any treatment-emergent AE leading to discontinuation of study drugs (atogepant and ubrogepant)

- Any treatment-emergent AE leading to death
- All deaths

10.2.3 Treatment-Emergent Adverse Events by SOC and/or PT

Treatment-emergent adverse events will be summarized, for each treatment period and overall, by SOC and PT; by maximum relationship to study drug as assessed by the investigator (e.g., reasonable possibility or no reasonable possibility) and SOC and PT; by maximum severity and SOC and PT. Specific adverse events will be counted once for each subject for calculating percentages, unless stated otherwise. In addition, if the same adverse event occurs multiple times within a subject, the highest severity and level of relationship to investigational product will be reported.

The incidence of common ($\geq 2\%$ and $\geq 5\%$ [after rounding] of subjects) TEAEs will be summarized by preferred term for each treatment period and overall.

Kaplan-Meier Curves will be provided for the time to the occurrence of certain AEs (nausea, constipation, fatigue/somnolence, decrease appetite) for the entire open-label treatment period.

10.2.4 SAEs (Including Deaths) and Adverse Events Leading to Study Drug Discontinuation

The number and percentage of subjects in the Safety Population 1 and Safety Population 2 who have SAEs (including deaths) and AEs leading to study drug discontinuation will be summarized by SOC and PT.

In addition, the list for SAEs (including deaths) and AEs leading to study intervention discontinuation will be provided.

10.2.5 Adverse Events of Special Interest

All AEs of special interest must be reported within 24 hours of the time the investigator becomes aware of the event using the AE eCRF and the hepatic eCRF.

The following AEs of special interest will be monitored during the study:

- Treatment-emergent elevated ALT or AST laboratory value $\geq 3 \times$ ULN.
- Potential Hy's law cases: elevated ALT or AST laboratory value $\geq 3 \times$ ULN and an elevated total bilirubin laboratory value $\geq 2 \times$ ULN and, at the same time, an alkaline phosphatase laboratory value $< 2 \times$ ULN.

10.3 Laboratory Data

Data collected from central laboratories, including additional laboratory testing due to an SAE, will be used in all analyses, except for Baseline where SAE-related laboratory assessments on or before the first dose of study drug without timestamp will be excluded. The details for SAE-related laboratory baseline can be found in the SPP. The clinical laboratory tests defined in the protocol (e.g., hematology, clinical chemistry and urinalysis) will be summarized.

Each laboratory variable will be summarized for all time points (starting with Baseline) with the number of non-missing observations, mean and standard deviation, median, Q1, Q3, minimum and maximum. Mean change from baseline to each applicable post-baseline visit will be summarized with the number of observations, baseline mean, and visit mean. The change from baseline mean, standard deviation, median, Q1, Q3, minimum and maximum will be presented for the mean change from baseline. In addition, descriptive statistics for values and changes from the baseline values in conventional units at each assessment time point will be presented for selected clinical laboratory parameters listed in Appendix D. A description of reporting the lab values in conventional units in patient narratives (along with the standard reporting in SI units) is presented at the end of Appendix D.

Changes in laboratory parameters will be summarized using shift tables categorized as low, normal, or high based on the normal ranges of the laboratory used for each sample. A shift table will be provided to summarize shifts from baseline to the final post-baseline value for all lab categories.

Laboratory abnormalities will be evaluated based on potentially clinically significant (PCS) criteria (Table 4). For each laboratory PCS criterion, the number and percentage of subjects who have a laboratory value meeting the criteria will be summarized in Safety Populations 1 and 2 for each treatment period and overall. Listings will be provided to summarize subject-level laboratory data for subjects meeting PCS criteria.

The number and percentage of subjects meeting each of the criteria for postbaseline hepatic laboratory abnormalities listed in Table 5 will be summarized. The percentages will be calculated relative to the number of subjects with at least 1 available postbaseline assessment. The numerator will be the total number of subjects having at least 1 postbaseline value that meets the specific category during the study. A supportive listing will also be provided.

The number and percentage of subjects with an adjudicated case (i.e., ALT \geq 3 x ULN and/or AST \geq 3 x ULN) will be summarized by relationship of ALT or AST elevation to study medication. The percentages will be calculated relative to the number of subjects with at least 1 adjudicated case. The numerator will be the number of subjects with at least 1 adjudicated case in the specific category of relationship. If a subject has more than 1 adjudicated case, he or she will be counted in the most relevant category of relationship.

Subjects with an adjudicated case (i.e., ALT \geq 3 x ULN or AST \geq 3 x ULN) will be listed with their ALT and AST assessments, adjudication dates, relationship of ALT or AST elevation to study medication, and confounding factor(s). Additional listings will be provided for subjects who meet ALT \geq 3 x ULN or AST \geq 3 x ULN and/or potential Hy's law and have one of the following categories: at least 1 abnormal liver biochemistry risk factor, at least 1 liver disease sign and symptom, at least 1 liver diagnostic test performed, consultation with a specialist for liver evaluation, liver lab tests performed, and drug screen performed, respectively.

Potential Hy's Law criteria within a 24-hour window is defined by a postbaseline evaluation of alanine aminotransferase (ALT) or aspartate aminotransferase (AST) \geq 3 x ULN, along with total bilirubin (TBL) \geq 2 x ULN and a non-elevated alkaline

phosphatase (ALP) < 2 x ULN, all based on blood draws collected within a 24-hour period. Patients who meet the potential Hy's Law criteria will be summarized. Supportive listing will also be provided.

A listing of urine pregnancy test results will be provided for female subjects of child-bearing potential with at least one positive result.

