There will be a total of 9 scheduled clinic visits: Screening/Visit 1 (Week -1), Baseline/Visit 2 (Day 1), Visit 3 (Week 4), Visit 4 (Week 8), Visit 5 (Week 12), Visit 6 (Week 16), Visit 7 (Week 20), Visit 8/Early Termination (Week 24), and Visit 9/Safety Follow-up (Week 28).

The total duration of study participation is 29 weeks. Total treatment duration is 24 weeks. See Section 5 for information regarding eligibility criteria.

All subjects who take at least 1 dose of atogepant 60 mg will enter a safety follow-up period of 4 additional weeks after their last dose of study drug. All subjects, regardless of the number of doses of study drug which are self-administered, should complete Visit 8/Early Termination and Visit 9 (Safety Follow-up), unless the subject has withdrawn consent. An interim analysis that includes all safety and efficacy analyses is planned. Details are provided in Section 7.6.

The schematic of the study is shown in [Figure 1](#). Further details regarding study procedures are located in the Operations Manual ([Appendix F](#)).

Figure 1. Study Design

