APPENDIX D. ACTIVITY SCHEDULE

The following table shows the required activities. The individual activities are described in detail in the Operations Manual ([Appendix F](#)).

Study Activities Table

Activity	Visit 1 Screening	Visit 2 Baseline	Visit 3	Visit 4	Visit 5	Visit 6	Visit 7	Visit 8 OR Early Termination	Visit 9 Safety Follow-Up Visit
	Week -1	Day 1 +3days	Week 4 ±3days	Week 8 ±3days	Week 12 ±3days	Week 16 ±3days	Week 20 ±3days	Week 24 +3days	Week 28 ±3days
❑ INTERVIEWS & QUESTIONNAIRES									
Informed consent	✓								
Eligibility criteria	✓	✓							
Medical/surgical history	✓								
Migraine history	✓								
Adverse event assessment	✓	✓	✓	✓	✓	✓	✓	✓	✓
Prior/concomitant therapy	✓	✓	✓	✓	✓	✓	✓	✓	✓
Patient-reported outcomes: HIT-6		✓	✓	✓	✓	✓	✓	✓	
Patient-reported outcomes: MSQ v2.1	✓	✓	✓	✓	✓	✓	✓	✓	
Patient-reported outcomes: WPAI:MIGRAINE		✓	✓	✓	✓	✓	✓	✓	
Patient-reported outcomes: PGIC (atogepant)					✓				
Patient-reported outcomes: PGIC (atogepant + ubrogepant)								✓	
Patient-reported outcomes: PHQ-4		✓	✓	✓	✓	✓	✓	✓	
Patient-reported outcomes: MTOQ-6						✓	✓	✓	
Patient-reported outcomes: Subject satisfaction with atogepant					✓			✓	
Patient-reported outcomes: subject satisfaction with ubrogepant								✓	

	Visit 1 Screening	Visit 2 Baseline	Visit 3	Visit 4	Visit 5	Visit 6	Visit 7	Visit 8 OR Early Termination	Visit 9 Safety Follow-Up Visit
Activity	Week -1	Day 1 +3days	Week 4 ±3days	Week 8 ±3days	Week 12 ±3days	Week 16 ±3days	Week 20 ±3days	Week 24 +3days	Week 28 +3days
Patient-reported outcomes: subject satisfaction with atogepant & ubrogepant								✓	
Investigator interviewer questionnaire migraine - screening	✓								
Investigator interviewer questionnaire migraine - Visit 2-5		✓	✓	✓	✓				
Investigator interviewer questionnaire migraine - Visit 6-8						✓	✓	✓	
C-SSRS	✓	✓	✓	✓	✓	✓	✓	✓	✓
LABORATORY & SITE EXAMINATIONS									
12-lead ECG	✓				✓			✓	
Height (screening only) and weight	✓	✓	✓	✓	✓	✓	✓	✓	✓
Vital signs	✓	✓	✓	✓	✓	✓	✓	✓	✓
Physical examination	✓							✓	✓
Urine pregnancy test	✓	✓	✓	✓	✓	✓	✓	✓	✓
CENTRAL LABORATORY									
Clinical laboratory tests	✓	✓	✓	✓	✓	✓	✓	✓	✓
PK (optional): predose at Visit 2		✓		✓				✓	
Biomarker samples (optional): predose at Visit 2		✓		✓				✓	✓
Pharmacogenetic sample – blood (optional)	✓								
Rx TREATMENT									
IRT entry	✓	✓	✓	✓	✓	✓	✓	✓	
Dispense study drug (atogepant)		✓	✓	✓	✓	✓	✓		
Dispense study drug (ubrogepant)					✓	✓	✓		
Perform drug reconciliation			✓	✓	✓	✓	✓	✓	

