10.5 Other Safety Analyses

10.5.1 Electrocardiogram

Descriptive statistics for ECG parameters (i.e., heart rate, PR interval, QRS interval, RR interval, QT interval, and QTc interval) at baseline, postbaseline, and changes from baseline values at each postbaseline timepoint will be presented for the Safety Populations 1 and 2.

ECG parameter values are considered PCS if ECG values meet either the actual value or change from baseline PCS high criteria listed in Table 7. The number and percentage of subjects with PCS postbaseline values will be summarized. The percentages will be calculated relative to the number of subjects with an available non-PCS baseline value and at least 1 postbaseline assessment. The numerator will be the total number of subjects with an available non-PCS baseline value and at least 1 PCS postbaseline ECG value during the study. A supportive listing of subjects with PCS postbaseline values will be provided. A listing of all AEs for participants with PCS ECG values will also be provided.

The number and percentage of subjects meeting each of the criteria for postbaseline ECG values of clinical interest listed in Table 5 will be summarized. Subjects will be counted only once for the most severe category. A supportive listing of participants with postbaseline QTcF increases > 30 msec will be provided, including the PID number, study center, and all QTc values (including changes from baseline). A listing of all AEs for participants with postbaseline QTcF increases > 30 msec will also be provided.

A shift table from baseline to the end of open-label treatment period in the investigator's overall interpretation of the ECG will be presented for the following categories: normal; abnormal, not clinically significant; abnormal, clinically significant. A tabular display of subjects with postbaseline clinically significant ECG abnormalities according to the investigator's overall interpretation will be provided.

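### The laboratory shift table has no treatment-period cut-off, so for subjects who attend Visit 9 it reports a value taken about 4 weeks after dosing stopped

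*SAP*

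**What the plan says.** SAP 10.3 classifies laboratory values as low, normal or high and then states: "A shift table will be provided to summarize shifts from baseline to the final post-baseline value for all lab categories". It does not define that last value by visit, by treatment period or by distance from the last dose. The same section says: "Data collected from central laboratories, including additional laboratory testing due to an SAE, will be used in all analyses". The only exception it makes concerns certain SAE-related samples at baseline. Nothing removes follow-up samples.

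In protocol Appendix D (the activity schedule, not SAP Appendix D, which lists conventional units), the row "Clinical laboratory tests" is ticked at all nine visits, including Visit 9. Protocol 4.1 states "Total treatment duration is 24 weeks", places Visit 9 at Week 28, and says that subjects who took atogepant "will enter a safety follow-up period of 4 additional weeks after their last dose of study drug". It expects every subject to complete Visit 9 unless consent is withdrawn. Protocol 5.6 sends early terminators to Visit 9 four weeks after their Early Termination Visit.

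**The concern.** Laboratory testing is part of the primary endpoint (SAP 3.1), and the primary objective is the safety of taking the two drugs together. A shift table is normally read as showing how many subjects moved out of the normal range on treatment. If its end point is a sample drawn after both drugs have stopped, it answers a different question. A subject who was normal at baseline, high at Visit 8 and normal again at Visit 9 is tabulated as normal to normal. A subject who was normal throughout treatment and high only at Visit 9 is tabulated as a shift. A reader of the table could not tell either case from a true on-treatment result.

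**Working it through.** **1. Timing.** The stated participation of 29 weeks reproduces: 1 (screening) + 24 (treatment) + 4 (follow-up) = 29.

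- Visit 8: 24 × 7 = day 168. Visit 9: 28 × 7 = day 196. Nominal gap: 196 − 168 = 28 days.
- With the printed windows (Visit 8 +3 days, Visit 9 ±3 days), the shortest gap is (196 − 3) − (168 + 3) = 22 days and the longest is (196 + 3) − 168 = 31 days. The continuation page of the schedule prints +3 for Visit 9, which would raise the minimum to 196 − 171 = 25.
- Early terminators: 28 days after the Early Termination Visit. Protocol 5.6 prefers that visit within 2 weeks, so the gap from the last dose can be about 28 + 14 = 42 days.

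**2. Which value the table takes, read literally.**

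| Subject | Last post-baseline sample | Status |
|---|---|---|
| Completer, attends Visit 9 | Visit 9 | about 4 weeks after dosing |
| Completer, misses Visit 9 | Visit 8 | end of treatment |
| Early terminator, attends Visit 9 | Visit 9 | about 4 to 6 weeks after dosing |
| Early terminator, misses Visit 9 | Early Termination or earlier | on treatment, or up to about 2 weeks after |

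**3. What the other planned laboratory outputs cover.**

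- By-visit summaries and changes from baseline (SAP 10.3) include Visit 8, but as means and quantiles, not as counts of subjects who changed category.
- PCS counts are given by treatment period and overall, but most thresholds lie well outside the normal range. SAP Table 4 uses creatinine > 1.5 × ULN, creatine kinase > 2.0 × ULN and neutrophils < 0.7 × LLN.
- SAP Table 5 counts any post-baseline value from 1 × ULN upwards, but only for liver tests.
- Subject listings (SAP 3.3) hold the raw values without tabulating them.

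For example, creatinine at 1.2 × ULN at Visit 8 and back in range at Visit 9 is not PCS, is not in Table 5, and appears as no shift.

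**4. Illustration of size and direction (all rates assumed; the documents give none).** Let p be the true end-of-treatment shift rate, a the Visit 9 attendance, r the share of shifts that reverse by Visit 9, and q the rate of new shifts at Visit 9 among subjects who had none. Non-attenders contribute their end-of-treatment value. Then

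shown = p(1 − a·r) + (1 − p)·a·q.

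With p = 5%, a = 90% and q = 0:

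| r | shown |
|---|---|
| 0 | 5.0% |
| 25% | 5 × (1 − 0.225) = 3.9% |
| 50% | 5 × (1 − 0.45) = 2.8% |
| 75% | 5 × (1 − 0.675) = 1.6% |

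Losses and gains cancel when q = p·r/(1 − p). At p = 5% this is 0.0125/0.95 = 1.3% for r = 25%, 0.025/0.95 = 2.6% for r = 50%, and 0.0375/0.95 = 3.9% for r = 75%. Above that q the table overstates the on-treatment rate; below it, the table understates.

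**The case against.** SAP 10.3 never names Visit 9. The result follows from an undefined term combined with the schedule, and a programming document could restrict it. The SAP refers to one, the SPP, but only for the SAE-related laboratory baseline, and it is not available here. This point stands as a caution. It does not remove the need for the rule to be in the SAP.

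Visit 9 also lies nominally inside the 30-day window that SAP 10.2.1 uses for treatment-emergent events, so the plan treats the interval as relevant to safety. That rule is for adverse events, where counts accumulate. A last-value table instead replaces the Visit 8 result with the Visit 9 result, so the window does not justify it.

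On-treatment abnormalities are captured elsewhere, as shown above, and laboratory changes that lead to discontinuation or intervention, or that the investigator judges to be adverse events, are reported as such (Protocol 6.1). This stands and limits the reach to one descriptive table.

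Three stronger readings are tempting, and the documents do not support them.

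- A reader might infer that the SAP contradicts itself, because SAP 10.5.1 specifies "A shift table from baseline to the end of open-label treatment period in the investigator's overall interpretation of the ECG". But protocol Appendix D schedules ECGs only at Visits 1, 5 and 8. With no ECG at Visit 9, that wording fits the collection schedule and is not evidence of a conflicting rule.
- A reader might infer that the table is wholly off-drug. It is mixed, because non-attenders contribute earlier values. The documents give no half-lives or recovery times, so all that is known is that dosing has stopped.
- A reader might infer that the table understates laboratory effects. That holds for reversible effects, but new shifts at Visit 9 act the other way.

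**Conclusion.** The point holds as a defect in one table. Followed literally, SAP 10.3 replaces the end-of-treatment value with a post-treatment one for every subject who has a Visit 9 sample, nominally 28 days after Visit 8 (22 to 31 days by the printed windows). It uses earlier values for the rest. Reversible shifts at Visit 8 can be lost and shifts arising after treatment can be counted. The net direction and size cannot be derived from the documents, and the percentages above are illustrations on assumed rates.

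What is at stake is the tabulation of low/normal/high shifts that fall short of the PCS thresholds, mainly for non-hepatic parameters, where no other planned categorical output covers them. The laboratory assessment as a whole is not compromised. The conclusion assumes that no programming document outside the SAP already limits the term to the treatment period.

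**What to change.** In SAP 10.3, define the shift end point as the last value in the treatment period, using a stated window relative to the last dose of study drug. For completers this is nominally Visit 8, so the window must admit the Visit 8 visit window. For early terminators it is the Early Termination sample only if that falls inside the window. A cut-off worded simply as through Visit 8/Early Termination would not be enough, because that visit may come up to about 2 weeks after the subject stops. Since ubrogepant is taken as needed, the sentence should also say which drug's last dose anchors the window.

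Show Visit 9 as a separate follow-up shift. A shift from baseline to the worst on-treatment value is an optional addition.

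The cost is one sentence in the SAP and one or two extra tables from data already collected. Sample size and study conduct do not change.

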5 STUDY ACTIVITIES

5.1 Eligibility Criteria

Subjects must meet all of the following criteria in order to be included in the study. Anything other than a positive response to the questions below will result in exclusion from study participation.

Consent

- 1. Subjects must voluntarily **sign and date an informed consent**, approved by an independent ethics committee (IEC)/institutional review board (IRB), prior to the initiation of any screening or study-specific procedures.

Demographic and Laboratory Assessments

- 2. **Male or female** subjects ages 18 to 80 years, inclusive, at Visit 1.
- 3. Must not have clinically significant **laboratory values** OR any of the following criteria at Visit 1:
 - ALT or AST > 1 × ULN;
 - total bilirubin > 1 × ULN (except for subjects with a diagnosis of Gilbert's disease); OR

- serum albumin < 2.8 g/dL.
- ✓ 4. Are willing and able to comply with procedures required in this protocol.

Disease/Condition Activity

- ✓ 5. At least a 1-year history of migraine with or without aura consistent with a diagnosis according to the International Classification of Headache Disorders (ICHD)-3, 2018. (See Section 7.1 of the Operations Manual).
- ✓ 6. Age of the subject at the time of migraine onset < 50 years.
- ✓ 7. History of 4 to 14 **migraine** days per month (see Section 3.4 of the Operations Manual for definition of migraine day) on average in the 3 months prior to Screening/Visit 1 in the investigator's judgment.
- ✓ 8. History of less than 15 **headache** days per month (see Section 3.4 of the Operations Manual for definition of headache day) on average across the 3 months prior to Screening/Visit 1 in the investigator's judgment.
- ✓ 9. Able to distinguish migraine headaches from tension-type or other headaches.

Subject History

- ✓ 10. No history of migraine accompanied by diplopia or decreased level of consciousness or retinal migraine as defined by ICHD-3, 2018. (See Section 7.1 of the Operations Manual)
- ✓ 11. No current diagnosis of chronic migraine, new persistent daily headache, trigeminal autonomic cephalgia (e.g., cluster headache), or painful cranial neuropathy as defined by ICHD-3, 2018.

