Laboratory Parameter	Categories
ALT	≥ 1 × ULN
	≥ 1.5 × ULN
	≥ 2 × ULN
	≥ 3 × ULN
	≥ 5 × ULN
	≥ 10 × ULN
	≥ 20 × ULN

Laboratory Parameter	Categories
AST	$\geq 1 \times \text{ULN}$
	$\geq 1.5 \times \text{ULN}$
	$\geq 2 \times \text{ULN}$
	$\geq 3 \times \text{ULN}$
	$\geq 5 \times \text{ULN}$
	$\geq 10 \times \text{ULN}$
	$\geq 20 \times \text{ULN}$
ALT or AST	$\geq 1 \times \text{ULN}$
	$\geq 1.5 \times \text{ULN}$
	$\geq 2 \times \text{ULN}$
	$\geq 3 \times \text{ULN}$
	$\geq 5 \times \text{ULN}$
	$\geq 10 \times \text{ULN}$
	$\geq 20 \times \text{ULN}$
Bilirubin Total	$\geq 1 \times \text{ULN}$
	$\geq 1.5 \times \text{ULN}$
	$\geq 2 \times \text{ULN}$
	$\geq 3 \times \text{ULN}$
	$\geq 5 \times \text{ULN}$
	$\geq 10 \times \text{ULN}$
	$\geq 20 \times \text{ULN}$
Alkaline Phosphatase	$\geq 1 \times \text{ULN}$
	$\geq 1.5 \times \text{ULN}$
	$\geq 2 \times \text{ULN}$
	$\geq 3 \times \text{ULN}$
	$\geq 5 \times \text{ULN}$
	$\geq 10 \times \text{ULN}$
	$\geq 20 \times \text{ULN}$
Concurrent Elevations ¹	ALT or AST $\geq 3 \times \text{ULN}$ and Bilirubin Total $\geq 1.5 \times \text{ULN}$
	ALT or AST $\geq 3 \times \text{ULN}$ and Bilirubin Total $\geq 2 \times \text{ULN}$
Potential Hy's Law ¹	ALT or AST $\geq 3 \times \text{ULN}$ and Bilirubin Total $\geq 2 \times \text{ULN}$ and ALP $< 2 \times \text{ULN}$

ALT = alanine aminotransferase; AST = aspartate aminotransferase; TBL = total bilirubin; ALP = alkaline phosphatase; ULN = upper limit of normal (value provided by the laboratory)

1. Elevations are from the same day.

Vital sign values will be considered PCS if they meet both the observed value criterion and the change from baseline value criterion, if both criteria are available, or meet either the observed value criterion or the change from baseline value criterion that is detailed in the following table.

Table 6. Potentially Clinically Significant Criteria for Vital Signs Parameters

Parameter	Flag	Criteria	
		Observed Value	Change from Baseline
Systolic blood pressure, mm Hg	High	≥ 180	Increase of ≥ 20
	Low	≤ 90	Decrease of ≥ 20
Diastolic blood pressure, mm Hg	High	≥ 105	Increase of ≥ 15
	Low	≤ 50	Decrease of ≥ 15
Pulse rate, bpm	High	≥ 120	Increase of ≥ 15
	Low	≤ 50	Decrease of ≥ 15
Weight, kg	High	—	Increase of $\geq 7\%$
	Low	—	Decrease of $\geq 7\%$
Orthostatic SBP change, mm Hg	Low	≤ -20	—
Orthostatic DBP change, mm Hg	Low	≤ -15	—
Orthostatic Pulse rate change, bpm	High	≥ 25	—

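### Laboratory PCS and hepatic category counts do not condition on baseline, so pre-existing abnormalities can be reported as on-treatment ones

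*SAP*

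**What the plan says.** **Table 4 (laboratory PCS).** SAP 10.3 states that "the number and percentage of subjects who have a laboratory value meeting the criteria will be summarized", reported "in Safety Populations 1 and 2 for each treatment period and overall". It gives no denominator and no condition on baseline, and does not restrict the count to postbaseline values.

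**Table 5 (hepatic categories).** Here SAP 10.3 gives the rule in full. For the denominator: "The percentages will be calculated relative to the number of subjects with at least 1 available postbaseline assessment". For the numerator: "The numerator will be the total number of subjects having at least 1 postbaseline value that meets the specific category during the study". Neither depends on the baseline value.

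**Other safety domains.** In SAP 10.5.1, ECG PCS percentages are taken "relative to the number of subjects with an available non-PCS baseline value and at least 1 postbaseline assessment", and the numerator carries the same baseline condition. For vital signs, SAP Appendix C says: "Vital sign values will be considered PCS if they meet both the observed value criterion and the change from baseline value criterion" where both criteria exist.

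**Entry criteria.** Protocol 5.1, criterion 3, excludes ALT or AST above 1 × ULN, total bilirubin above 1 × ULN ("except for subjects with a diagnosis of Gilbert's disease") and albumin below 2.8 g/dL at Visit 1. It also excludes values judged clinically significant. No bilirubin ceiling is given for Gilbert's subjects.

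**The concern.** Clinical laboratory testing is part of the primary endpoint (SAP 3.1). The study has no control group (Protocol 4.2), so no parallel arm shows the background frequency of abnormal values. Each subject's own baseline is the only reference, and the laboratory threshold tables do not use it.

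A subject who met a criterion before the first dose, and simply continues to meet it, can then appear in the same row as a subject who first crossed the threshold on treatment. A reader of the table cannot tell the two apart.

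The other planned outputs help only in part. The shift tables use low, normal and high, and go from baseline to the final value. They cannot show a new crossing of 1.5 or 2 × ULN within the high category, or an abnormality that resolved before the last visit. Mean changes do not identify individuals. The listings hold the information, but leave the reader to rebuild the counts by hand.

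**Working it through.** **1. Who can be affected.**

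- *Bilirubin.* Gilbert's subjects may enter above 1 × ULN. If that level continues after dosing, they meet the lowest Table 5 bilirubin row (≥ 1 × ULN) without any change. They meet the Table 4 row (≥ 1.5 × ULN) and the higher Table 5 rows only if their bilirubin is that high.
- *Parameters with no numeric entry limit.* These include eGFR (PCS below 60), cholesterol and triglycerides, creatine kinase, uric acid, alkaline phosphatase, urine glucose and urine protein. Protocol 5.1 admits subjects up to age 80, and criterion 16 allows disease stable for more than 1 year, including renal and endocrine disease, if the investigator judges it unlikely to interfere.
- *ALT and AST.* These are almost unaffected, because values above 1 × ULN at Visit 1 exclude. Two small routes remain. A value exactly at 1 × ULN passes entry yet meets the ≥ 1 × ULN row. Laboratory tests are also repeated at Visit 2, and that result can become the baseline.

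**2. Can the condition be applied?** Yes. SAP 10.1 defines the laboratory baseline as the last non-missing assessment before the first dose.

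**3. The plan's own numbers.** SAP 2.4 enrols 235 and assumes 15% discontinuation in the first period: 235 × (1 − 0.15) = 199.75, which reproduces the stated 200. The planned 95% CI half-width of about 3% to 5% for AEs also reproduces, taking 1.96 × √(p(1 − p)/n). At n = 200 this is 3.02% for p = 5% and 4.95% for p = 15%; these rates are my assumption. The point disputes no stated figure.

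**4. Size under assumed inputs.** For one table row let

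- b = share of subjects meeting the criterion at baseline,
- r = chance that such a subject meets it again postbaseline,
- e = chance that a subject not meeting it at baseline comes to meet it.

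As written, reading Table 4 as postbaseline, the expected rate is b·r + (1 − b)·e. With the ECG-type condition it is e. The non-emergent share of the count is b·r / [b·r + (1 − b)·e].

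The documents give none of b, r or e. With e = 1%, r = 0.8 and n = 235:

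| b | Rate as written | Subjects | Non-emergent share | With baseline condition |
|---|---|---|---|---|
| 1% | 0.80% + 0.99% = 1.79% | 4.2 | 45% | 2.3 of 232.65 = 1.0% |
| 3% | 2.40% + 0.97% = 3.37% | 7.9 | 71% | 2.3 of 227.95 = 1.0% |
| 5% | 4.00% + 0.95% = 4.95% | 11.6 | 81% | 2.2 of 223.25 = 1.0% |

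The percentages do not depend on n, so they are the same at 200.

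**5. Sensitivity.** With e = 2% and r = 0.8, the as-written rates are 2.78%, 4.34% and 5.90%. With e = 1% and r from 0.5 to 1.0, they run from 1.49% to 1.99% at b = 1%, and from 3.45% to 5.95% at b = 5%. Over b from 1% to 10%, r from 0.5 to 1.0 and e of 1% or 2%, the as-written rate is 1.2 to 10.9 times the emergent rate.

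**The case against.** The strongest reply is that this is a choice of convention with little consequence. The Table 5 output is described as postbaseline abnormalities, not treatment-emergent ones, and an inclusive liver table can be deliberate. SAP 10.5.1 itself counts ECG values of clinical interest (Table 8) with no stated baseline exclusion, so the SAP already uses more than one rule. The analyses are descriptive, with no test or numeric safety limit, and the error overstates abnormality, which is the cautious direction. Reporting by treatment period also suggests that only on-treatment values are meant for Table 4.

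Much of this stands. It is a reason to keep the inclusive hepatic table, and to call the difference from ECG PCS an inconsistency of convention rather than a contradiction. It does not justify leaving laboratory PCS without a denominator or baseline rule when ECG PCS has both. Nor is overstatement harmless: a row made up mostly of pre-existing abnormality is a poor place to see a new one.

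A reader might infer three stronger things that the documents do not support:

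- *That the adverse events of special interest are inflated.* These are ALT/AST ≥ 3 × ULN and potential Hy's law (SAP 10.2.5). The entry limit on ALT/AST keeps nearly all baseline cases out, and raised bilirubin alone is not one of these events.
- *That Gilbert's subjects will fill the bilirubin rows.* The protocol only exempts them from the entry limit. It does not say that any will be enrolled, or that any reach 1.5 or 2 × ULN.
- *That pre-dose samples are themselves counted.* For Table 5 the text limits the numerator to postbaseline values. For Table 4 the text is silent, and the reporting by period points the other way.

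**Conclusion.** The point holds in limited form. As written, SAP 10.3 can mix pre-existing with new abnormalities in the Table 4 PCS rows and in the Table 5 bilirubin and alkaline phosphatase rows. For Table 5 this follows from explicit text; for Table 4 it follows from the absence of a rule.

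The size cannot be fixed from the documents. The rise from 1% to between 1.79% and 4.95% rests on assumed baseline prevalence (1% to 5%), emergent incidence (1%) and persistence (80%), and will differ by parameter. At the upper end the excess is 4.95 − 1.00 = 3.95 percentage points, within the 3% to 5% half-width that the plan sets as its precision for AEs. That is enough to matter in a single-arm safety study, so the change is worth making even though no hypothesis test depends on it.

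**What to change.** **Table 4.** State the ECG rule in SAP 10.3. The denominator is subjects with an available non-PCS baseline for that criterion and at least 1 postbaseline value. The numerator is those among them with at least 1 postbaseline PCS value. List subjects who were PCS at baseline separately.

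**Table 5.** Keep the all-postbaseline table. Add an emergent count restricted to subjects not meeting the category at baseline, or split each row by baseline status with Gilbert's subjects flagged.

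**Cost.** SAP wording and a little programming, using a condition already specified for ECG. No new data and no change to study conduct. Denominators become row-specific and slightly smaller, for example 223.25 instead of 235 at an assumed 5% baseline prevalence.

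**Limit.** The baseline is the single pre-study one. An abnormality that first appears in the atogepant period and persists would still count in both periods; if that matters, it needs its own rule.
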